#### Phase IIa Exclusion Criteria

- Untreated or symptomatic CNS metastases.  
*Note:* Patients with treated and asymptomatic CNS metastases that are radiographically stable within 12 weeks prior to enrollment will be allowed, provided long-term use of corticosteroids have been discontinued within 4 weeks prior to enrollment
- Patients with a history of endometrial polyps, endometrial cancer, atypical endometrial hyperplasia, or other significant endometrial disorders should be excluded unless they have undergone total hysterectomy and there is no evidence of active disease.

- Prior treatments:

EXCLUSIONS	Prior Endocrine Therapy	Prior Chemotherapy
Cohort A1	▪ Fulvestrant	▪ > 1 prior chemotherapy in the advanced/metastatic setting
Cohort A2		▪ > 1 prior chemotherapy in the advanced/metastatic setting
Cohort B1	▪ > 1 prior AI in the advanced/metastatic setting ▪ Fulvestrant	▪ Prior chemotherapy in the advanced/metastatic setting (prior adjuvant chemotherapy is allowed so long as it occurred $\geq$ 12 months prior to enrollment)
Cohort B2	▪ > 1 prior AI in the advanced/metastatic setting	▪ > 1 prior chemotherapy in the advanced/metastatic setting

- Current treatment with any systemic anti-cancer therapies for advanced disease
- Diagnosis of any secondary malignancy within 2 years prior to enrollment, except for adequately treated basal cell or squamous cell skin cancer, or carcinoma in situ
- Any of the following within 12 months prior to enrollment: myocardial infarction, severe/unstable angina, ongoing cardiac dysrhythmias of Grade  $\geq$  2, atrial fibrillation of any grade, coronary/peripheral artery bypass graft, symptomatic congestive heart failure, or cerebrovascular accident including transient ischemic attack
- Active inflammatory bowel disease (e.g. Crohn's disease or ulcerative colitis), any active bowel inflammation (including diverticulitis), chronic diarrhea, short bowel syndrome, or history of upper gastrointestinal surgery including gastric resection
- Known human immunodeficiency virus infection
- Known clinically significant history of liver disease consistent with Child-Pugh Class B or C, including active viral or other hepatitis (e.g., Hepatitis B or Hepatitis C virus), current alcohol abuse, or cirrhosis
- Major surgery within 4 weeks prior to enrollment
- Radiation therapy within 2 weeks prior to enrollment
- Other severe acute or chronic medical or psychiatric condition or laboratory abnormality that may increase the risk associated with study participation or investigational product administration or may interfere with the interpretation of study results and, in the judgment of the Investigator, would make the subject inappropriate for entry into this study

#### Phase Ib Inclusion Criteria

- Histologically or cytologically proven diagnosis of adenocarcinoma of the breast with evidence of either locally recurrent disease not amenable to resection or radiation therapy with curative intent, or metastatic disease
- Documented sensitivity to prior hormonal therapy (Relapsed after 24 mo of adjuvant endocrine therapy or had a clinical benefit from prior endocrine therapy in the context of advanced disease)

- ER-positive tumor (staining in  $\geq 1\%$  cells by immunohistochemistry [IHC] as per local laboratory testing)
- HER2-negative breast cancer as per local laboratory testing (IHC result of 0 or +1 for cellular membrane protein expression or a FISH result showing HER2/CEP17 ratio  $< 1.8$  or an average of fewer than 4 copies of HER2 gene per nucleus for systems without an internal control probe)
- At least 2 weeks must have elapsed from the use of any other anti-cancer hormonal therapy excluding LHRH agonist for patients enrolled in Cohorts C3, D1 and D2
- At least 3 weeks must have elapsed from the use of any chemotherapy
- Females, 18 years of age or older
- Postmenopausal status defined as:
  - Prior bilateral surgical oophorectomy
  - Age  $\geq 56$  years: natural amenorrhea with  $\geq 1$  year since last menses
  - Age  $< 56$  years with amenorrhea  $\geq 1$  year since last menses and serum estradiol levels ( $< 20$  pg/mL) and follicle stimulating hormone (FSH) levels ( $> 40$  mIU/mL) in the postmenopausal range
  - Age  $< 56$  years who had hysterectomy with one or both ovaries left in place, or with tamoxifen-induced amenorrhea together with a tamoxifen discontinuation of  $\geq 1$  year and serum estradiol levels ( $< 20$  pg/mL) and FSH levels ( $> 40$  mIU/mL) in the postmenopausal range
  - Age  $< 56$  years who have medical menopause on LHRH agonist (on stable dose  $\geq 1$  year) with amenorrhea  $\geq 1$  year since last menses and serum estradiol levels in the postmenopausal range ( $< 20$  pg/mL) irrespective of FSH/LH levels; medical menopause is defined as ovarian suppression by any medical cause including treatment with LHRH agonist, radiation, or surgery causing inhibition of pituitary gonadotropin secretion, irrespective of FSH/LH levels.
  - Age  $< 56$  years who have medical menopause on LHRH agonist (on stable dose  $\geq 1$  month) for Phase Ib Cohorts D1, D2, and C3
- Eastern Cooperative Oncology Group (ECOG) performance status  $< 2$
- Resolution of all acute toxic effects of prior therapy or surgical procedures to baseline or Grade  $\leq 1$  (except alopecia or other toxicities not considered to be a safety risk for the patient)
- Adequate organ function as defined by the following criteria:
  - Absolute neutrophil count (ANC)  $\geq 1500/\mu\text{L}$
  - Platelets  $\geq 100,000/\mu\text{L}$
  - Serum aspartate transaminase (AST) and serum alanine transaminase (ALT)  $\leq 3$  times the upper limit of normal (ULN) or AST and ALT  $\leq 5 \times$  ULN if liver function abnormalities are due to underlying malignancy or liver metastasis
  - Total serum bilirubin  $\leq 1.5 \times$  ULN regardless of liver involvement secondary to tumor. Inclusion of patients with increased serum indirect bilirubin ( $\leq 3 \times$  ULN) due to Gilbert's syndrome is permitted.
  - Serum creatinine  $\leq 1.5 \times$  ULN
  - QTc  $\leq 460$  msec
- Signed and dated informed consent document indicating that the subject (or legally acceptable representative) has been informed of all the pertinent aspects of the trial prior to enrollment
- Willingness and ability to comply with scheduled visits, treatment plan, laboratory tests, and other trial procedures

- For women of childbearing potential (including patients with menopause induced by LHRH agonists): agreement to remain abstinent (refrain from heterosexual intercourse) or use non-hormonal contraceptive methods that result in a failure rate of < 1% per year during the treatment period and for at least 90 days after the last dose of LHRH agonist or 28 days after the last dose of GDC-0810 and palbociclib (whichever is latest)
 

A woman is considered to be of childbearing potential if she is postmenarcheal, has not reached a postmenopausal state ( $\geq 12$  continuous months of amenorrhea with no identified cause other than menopause), and has not undergone surgical sterilization (removal of ovaries and/or uterus).

Examples of non-hormonal contraceptive methods with a failure rate of < 1% per year include bilateral tubal ligation and copper intrauterine devices.

The reliability of sexual abstinence should be evaluated in relation to the duration of the clinical trial and the preferred and usual lifestyle of the patient. Periodic abstinence (e.g., calendar, ovulation, symptothermal, or postovulation methods) and withdrawal are not acceptable methods of contraception.
- Additional inclusion criteria for Cohorts C0, C1, C2, and C3 (palbociclib combination cohorts): No prior treatment with CDK4/6 inhibitor

#### Phase Ib Exclusion Criteria

- Untreated or symptomatic CNS metastases.
 

Note: Patients with treated and asymptomatic CNS metastases that are radiographically stable within 12 weeks prior to enrollment will be allowed, provided long-term use of corticosteroids have been discontinued within 4 weeks prior to enrollment.
- Patients with a history of endometrial polyps, endometrial cancer, atypical endometrial hyperplasia, or other significant endometrial disorders should be excluded unless they have undergone total hysterectomy and there is no evidence of active disease.
- More than two prior chemotherapies including adjuvant chemotherapy
- Current treatment with any systemic anti-cancer therapies for advanced disease or any systemic experimental treatment on another clinical trial
- Diagnosis of any secondary malignancy within 2 years prior to enrollment, except for adequately treated basal cell or squamous cell skin cancer, or carcinoma in situ
- Any of the following within 12 months prior to enrollment: myocardial infarction, severe/unstable angina, ongoing cardiac dysrhythmias of Grade  $\geq 2$ , atrial fibrillation of any grade, coronary/peripheral artery bypass graft, symptomatic congestive heart failure, or cerebrovascular accident including transient ischemic attack
- Active inflammatory bowel disease (e.g. Crohn's disease or ulcerative colitis), any active bowel inflammation (including diverticulitis), chronic diarrhea, short bowel syndrome, or history of upper gastrointestinal surgery including gastric resection
- Known human immunodeficiency virus (HIV) infection
- Known clinically significant history of liver disease consistent with Child-Pugh Class B or C, including active viral or other hepatitis (e.g., hepatitis B or hepatitis C virus), current alcohol abuse, or cirrhosis
- Major surgery within 4 weeks prior to enrollment
- Radiation therapy within 2 weeks prior to enrollment
- Other severe acute or chronic medical or psychiatric condition or laboratory abnormality that may increase the risk associated with study participation or investigational product administration or may interfere with the interpretation of study results and, in the judgment of the investigator, would make the subject inappropriate for entry into this study
- Pregnancy, lactation, or breastfeeding

- Additional exclusion criteria for patients in Cohorts C0, C1, C2 or C3 (palbociclib combination cohorts)
  - History of venous thromboembolic event requiring therapeutic anticoagulation
  - Vaginal bleeding within 2 months prior to enrollment

### **End of Study**

The end of this study is defined as the date when the last patient, last visit (LPLV) occurs, *GDC-0810 drug supply is exhausted, or when Sponsor decides to stop the study.*

### **Length of Study**

Study duration will be from April 2013 to *when GDC-0810 drug supply is exhausted, or when Sponsor decides to stop the study.*

### **Investigational Medicinal Products**

The research staff at each participating site will provide detailed instructions and training for the handling of the study drug (GDC-0810) and study treatment (palbociclib) and their administration to each patient at the beginning of her study participation.

All patients should take the full prescribed dose of GDC-0810 by mouth at approximately the same time each day and within 30 minutes after eating a meal. GDC-0810 tablets should be swallowed whole and tablets should not be cut or crushed.

Evening dosing may be initiated to alleviate gastrointestinal symptoms from GDC-0810. Please note that morning dosing the day before PK evaluation days is required to allow accurate assessment of PK trough levels of study drug.

If a dose is missed, patients should just take the next scheduled GDC-0810 dose, without compensating for the missed dose.

**Palbociclib (Phase Ib Cohorts C0 and C1):** Refer to palbociclib package insert for details on the formulation and storage of palbociclib. Palbociclib will be *supplied* by the Sponsor.

### **Phase Ia**

During Phase Ia, the full prescribed dose of GDC-0810 should be taken by mouth in the morning, after fasting overnight, at approximately the same time each day; food should not be eaten for at least 1 hour after taking GDC-0810. The dosing regimen may be changed if the PK and safety data from the dose escalation suggest that a discontinuous regimen or another dosing frequency (e.g., BID), with or without a fasting requirement, may be preferable for the Phase IIa portion of the study.

**PK Week Lead-In:** In Phase Ia, patients enrolled in the dose escalation cohorts will receive a single oral dose of GDC-0810 in the clinic on Day –7 and will return to the clinic for the next 2 consecutive days for PK sample collection. The time of dose administration will be called “0” (zero) hour. If a patient vomits after receiving GDC-0810, this should be recorded in the patient’s Case Report Form (CRF) but the dose should not be repeated.

In Phase Ib and Phase IIa, there will be no Day – 7 to Day 0 PK lead-in period.

**Continuous Dosing:** Phase Ia GDC-0810 will be given continuously beginning on Cycle 1 Day 1 in 28-day cycles. During Cycle 1 of the dose escalation, patients will return to the clinic on a weekly basis (Days 8, 15, and 22) for safety evaluation and collection of predose PK samples. On those days, treatment will be administered in the clinic.

Similarly, on Day 1 of every subsequent new cycle of dosing beginning with Cycle 2, study drug will be administered in the clinic following all the assessments as indicated in the Schedule of Activities.

All other doses of GDC-0810 will be administered on an outpatient basis. It is anticipated that some patients may occasionally forget to take a dose of GDC-0810. In those cases, patients should just take the next scheduled dose, without compensating for the missed dose.

### **Phase IIa**

The full bed dose of GDC-0810 should be taken by mouth at approximately the same time each day and within 30 minutes after eating a meal.

### **Phase Ib**

Palbociclib administration (if applicable): Palbociclib should be taken with food at the same time each day. The capsule should be swallowed whole. The capsules should not be chewed, crushed, or opened. If a dose is missed, patients should just take the next scheduled palbociclib dose, without compensating for the missed dose.

LHRH administration (if applicable): LHRH agonists should be administered monthly by site staff.

**Continuous Dosing:** In Phase Ib, GDC-0810 will be given continuously beginning on Cycle 1 Day 1 in 28-day cycles. During Cycle 1 of the dose escalation, patients will return to the clinic on a weekly basis (Days 8, 15, and 22) for safety evaluation and collection of predose PK samples. On those days, treatment will be administered in the clinic. Study treatments, palbociclib will be given on Days 1–21 of each cycle and LHRH agonist will be given on Day 1 of each cycle. Evening dosing may be initiated to alleviate gastrointestinal symptoms from GDC-0810. However, on Day 28 of Cycles 1, 2, and 3, the dose of GDC-0810 should be taken in the morning to allow trough PK sample collections on Cycle 2 Day 1, Cycle 3 Day 1, and Cycle 4 Day 1.

Similarly, on Day 1 of every subsequent new cycle of dosing beginning with Cycle 2, study treatment will be administered in the clinic following all the assessments as indicated in the Schedule of Activities.

All other doses of GDC-0810 or palbociclib will be administered on an outpatient basis. It is anticipated that some patients may occasionally forget to take a dose of GDC-0810 or palbociclib. In those cases, patients should just take the next scheduled dose, without compensating for the missed dose.

### **Non-Investigational Medicinal Products**

**Luteinizing Hormone Releasing Hormone Agonist (LHRH) (Phase Ib Cohort D1):** Choice of LHRH agonist will be an institutional choice approved for use in breast cancer. Refer to LHRH agonist package insert for details on the formulation and storage of LHRH agonist. If patient becomes intolerant to current LHRH agonist, then patient may switch to another approved LHRH agonist during trial. LHRH agonists will be prescribed by the study sites and cost of the study treatment will be reimbursed by the Sponsor for the duration of the study.

### **Statistical Methods**

#### **Primary Analysis**

##### **Phase Ia and Phase Ib**

For safety analyses, the analysis population will include all enrolled patients who receive at least one dose of study medication.

Study treatment discontinuation and reasons for patient discontinuations from the study will be described and summarized. Study drug administration data will be listed and any dose modifications will be flagged.

##### **Phase IIa**

Disease assessments (CT scan of the chest, abdomen, and pelvis, plus a bone scan) will be performed at screening and every 8 weeks from Cycle 1 Day 1 thereafter, regardless of treatment delays resulting from toxicity. Radiographic confirmation of objective tumor response or disease progression will be based on RECIST v1.1.

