## **PROTOCOL AMENDMENT, VERSION 9: RATIONALE**

Protocol GO29642 has been amended to reduce the number of required study procedures as a result of Sponsor decision to halt the development of GDC-0810 and halt enrollment into the study. The decision to halt the development of GDC-0810 is not due to any safety concerns. Adverse events observed for GDC-0810 alone or in combination with luteinizing hormone-releasing hormone (LHRH) agonist or palbociclib thus far are similar to those that have been observed with other endocrine agents and are amenable to monitoring, are manageable, and reversible.

As a result of the decision to halt development of GDC-0810, the following changes have been made:

- Enrollment in this study has been discontinued. Therefore, no further patients will be enrolled.
- Patients experiencing clinical benefit may continue to receive GDC-0810 as a single agent or in combination with LHRH agonist or palbociclib until progression of disease, unacceptable toxicity, consent withdrawal, GDC-0810 drug supply has been exhausted, or the Sponsor terminates the study.
- Limited Physical exam, ECOG, vital signs, liver function tests, creatinine, adverse events, concomitant medication, study drug compliance will be collected at least monthly and as clinically indicated.
- Hematology (for patients receiving GDC-0810 alone or in combination with LHRH agonist), blood chemistry (except creatinine and liver function tests), urinalysis, bone scans, and CT/MRI scans will be collected per institutional guidelines and as clinically indicated.
- Hematology will be collected at least monthly and as clinically indicated for patients receiving GDC-0810 in combination with palbociclib.
- The frequency of transvaginal ultrasounds has been changed from every 6 months to as clinically indicated due to the low rate of adverse events observed and to align with the other ongoing GDC-0810 study (GO29689). Collection of the transvaginal ultrasound at the end of treatment will continue.
- No new or potential safety risks have been identified; however, on the basis of accumulated clinical experience, dose modification guidelines have been updated.
- Collection of fasting lipid panel has been removed because it is not essential for ongoing safety monitoring.
- Clinical and nonclinical summaries have been update to align with the GDC-0810 Investigator's Brochure, Version 4.

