- The definition of the end of study has been revised because of the Sponsor's decision to halt the development of GDC-0810.
- Post-trial access to GDC-0810 has been revised because of the Sponsor's decision to halt the development of GDC-0810.

Additional minor changes have been made to improve clarity and consistency.  
Substantive new information appears in italics. This amendment represents cumulative changes to the original protocol.

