### **15.2.2 Phase IIa**

At the RP2D, a total of approximately 100 patients *have been* enrolled to further assess the safety, tolerability, preliminary evidence of anti-tumor activity, and exploratory PD markers of response of GDC-0810 in 3 distinct patient populations (Cohorts A1 and A2 will be combined for analysis purposes).

A total of 100 patients in Phase IIa will provide a more robust safety profile as well as sample size for preliminary assessment of anti-tumor activity based on clinical benefit rate (CBR) (see [Table 13](#)), defined as the percentage of patients achieving confirmed RECIST v1.1 defined complete response, partial response, and/or stable disease  $\geq 24$  weeks.

In Cohort A, because the presence of ESR1 mutations are associated with poor prognosis, an objective response rate (ORR), defined as the percentage of patients achieving confirmed complete and/or partial responses of at least 15% (5 out of 30 patients) would be considered of more clinical interest than CBR to warrant further development of GDC-0810 in this mutant patient population.

In Cohort B1, the desired observed CBR is 50%, based on historical CBRs of 46% ([Di Leo et al. 2010](#)) and 48% ([Bachelot et al. 2012](#)) for patients with ER+/HER2– advanced breast cancer after prior treatment with aromatase inhibitors.

In Cohort B2, the desired observed CBR is 20%, based on historical CBRs ranging from 18% to 26% for patients with ER+/HER2– advanced breast cancer after prior treatment with fulvestrant ([Baselga et al. 2011](#); [Yardley et al. 2013](#)).

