### **15.5 ANTI-TUMOR ACTIVITY**

Objective response and clinical benefit rates will be derived according to RECIST v1.1 and summarized by dose level and cohort. Progression-free survival will be listed for all patients in Phase IIa, when appropriate.

Objective response is defined as a complete response or partial response, as determined by investigator assessment and confirmed by repeat assessment  $\geq 4$  weeks after initial documentation. Patients with missing baseline or no response assessments will be classified as non-responders.

CBR is defined as the percentage of patients achieving confirmed RECIST v1.1-defined complete response, partial response, and/or stable disease  $\geq 24$  weeks.

Progression-free survival is defined as the time from the first day of study treatment with GDC-0810 in the Phase IIa until documented disease progression or death, whichever occurs first. For patients who do not have documented progressive disease or death before the end of the study or who are lost to follow-up, progression-free survival will be censored at the day of the last tumor assessment.

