## Appendix 2 Schedule of Activities: Phase IIa (cont.)

	Screening	Cycle 1	Cycles 2+ [1]	End of Treatment [1]	Safety Follow-Up (+ 2 days) [2]
Protocol Activities	≤ 28 days of 1 st dose	Day 1	Labs Biopsies, scans		
Tumor Biopsy (Cohort A patients, if feasible) [14]	X				
Archival Tissue Sample (optional) [15]	X				
Other Clinical Assessments					
ECOG and Vital Signs	X	X	X	X	(X)
Adverse Events/Con Meds and Treatments [16]	X	X	X	X	X
Transvaginal Ultrasound [17]	X		X	X	
Study Drug Compliance [18]			X	X	

Study assessments may be delayed or moved ahead of the window specified to accommodate holidays, vacations, and unforeseen delays.

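### Does Section 15.5 need a rule for which scan establishes stable disease of at least 24 weeks?

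*Combined protocol and SAP*

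**What the plan says.** The Synopsis (Statistical Methods, Primary Analysis, Phase IIa) states that CT and bone scans "will be performed at screening and every 8 weeks from Cycle 1 Day 1 thereafter, regardless of treatment delays resulting from toxicity".

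Section 15.5 reads: "CBR is defined as the percentage of patients achieving confirmed RECIST v1.1-defined complete response, partial response, and/or stable disease", followed by the limit of at least 24 weeks. Section 15.2.2 gives the same definition. Neither says from which date stable disease is counted, which scan must show it, or how far from week 24 that scan may lie.

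The neighbouring endpoints in Section 15.5 are specified more closely. Objective response needs confirmation at least 4 weeks later, and patients with no baseline or no response assessment are non-responders. Progression-free survival (PFS) runs from the first day of treatment "until documented disease progression or death, whichever occurs first", with censoring at the last tumor assessment.

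The note under the Appendix 2 schedule says: "Study assessments may be delayed or moved ahead of the window specified to accommodate holidays, vacations, and unforeseen delays". Appendix 2 gives no number of days for on-treatment scans.

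Section 15.2.2 hopes to observe a CBR of 50% in Cohort B1 (history 46% and 48%) and 20% in Cohort B2 (history 18% to 26%). Section 15.1 plans no confirmatory inference and no imputation.

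Under Version 9, "bone scans, and CT/MRI scans will be collected per institutional guidelines and as clinically indicated". Section 11.1.8 and Appendix 2 (footnotes 1 and 12) follow this; the Synopsis line does not.

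**The concern.** Anti-tumor activity is the Phase IIa primary objective, and CBR is the figure set beside history in Cohorts B1 and B2. With the third scan due on day 168, a scan one day early fails a literal reading of 24 weeks. Three readings of the same scans seem open:

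- **(a) Strict:** a scan on or after day 168 must show no progression.
- **(b) Windowed:** a scan close to week 24 that shows no progression is enough.
- **(c) Dated like PFS:** a patient whose progression is first seen on day 168 or later also has 24 weeks.

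The B1 target lies only 2 to 4 points above history, so the reading could move the observed rate from one side of history to the other. The study is open-label, and a convention fixed after the rates are known could look selected. Appendix 2 (footnote 2) also waives end-of-treatment imaging if a scan was done within 4 weeks. A patient scanned just before day 168 who then stops treatment may have no later scan to settle the matter.

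**Working it through.** **Reproducing the plan's figures.** Exact (Clopper-Pearson) 80% intervals:

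- B1, 25/50: 40.09% to 59.91%, width 19.8 points.
- B2, 4/20: 9.02% to 36.07%, width 27.0 points.

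Both match Table 13.

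**Scan days.** 3 × 8 × 7 = 168 days after Cycle 1 Day 1. The second scan is due at day 112 and the fourth at day 224.

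**Assumptions (not in the documents).** Time to progression is exponential, scaled so that the progression-free share at day 168 equals the CBR target: S(d) = p^(d/168), with p = 0.5 (B1) or 0.2 (B2). The third scan is spread evenly over days 161 to 175, so 7/15 = 46.7% of scans are early.

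| | S(112) | S(161) | S(168) | S(224) |
|---|---|---|---|---|
| B1 | 0.630 | 0.515 | 0.500 | 0.397 |
| B2 | 0.342 | 0.214 | 0.200 | 0.117 |

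**Formulas.**

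- (a) Mean of S(d) if d ≥ 168, otherwise S(224), because an early scan leaves the question to the fourth scan.
- (b) Mean of S(d).
- (c) Mean of S(112) if d ≥ 168, otherwise S(d).

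**Expected CBR, (a) / (b) / (c).**

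| Third-scan timing | B1 | B2 |
|---|---|---|
| Day 168 ± 7 | 44.8 / 50.0 / 57.3% | 15.8 / 20.0 / 27.9% |
| Day 168 ± 3 | 45.4 / 50.0 / 57.6% | 16.3 / 20.0 / 28.3% |
| All on day 168 | 50.0 / 50.0 / 63.0% | 20.0 / 20.0 / 34.2% |

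Confirmed responders count under every reading, which narrows the spread. With an assumed response rate of 20% in B1 the ± 7 row becomes 45.8 / 50.0 / 56.5%. With 10% in B2 it becomes 17.3 / 20.0 / 26.0%.

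**In patients.** Between (a) and (b) at ± 7 days: B1 5.2 points × 50 = 2.6 patients; B2 4.2 points × 20 = 0.8 patients.

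**Reading (c) is an upper bound.** It requires every progression between weeks 16 and 24 to be found only at the third scan. PFS also ends at death, and Section 12.2.5.9 allows clinical progression in rare cases. If 20% of those events were dated off schedule before day 168, the all-on-day-168 figures fall to 0.50 + 0.8 × (0.630 − 0.50) = 60.4% in B1 and 0.20 + 0.8 × (0.342 − 0.20) = 31.4% in B2.

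**What a written window would do.** Take an allowance of up to 7 days early, with every scan 7 days early. Against the model's true day-168 rate the gain is 51.5 − 50.0 = 1.5 points (B1) and 21.4 − 20.0 = 1.4 points (B2). That true rate is not what interval scans observe. Against the strict count, which is, the gain is 51.5 − 39.7 = 11.8 points and 21.4 − 11.7 = 9.7 points.

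**The case for a change.** The best case for acting is that the omission is genuine, cheap to repair and attached to the primary objective. Setting (c) aside, (a) and (b) still differ by about 5 points in B1, more than the 2 to 4 points that separate the target from history. Under (a), B1 falls below 48% once 2/10.31 = 19% of third scans are early, where 10.31 points is S(168) − S(224). Writing the convention down before the table is run would remove any suspicion of choice. The documents cite RECIST v1.1 but reproduce no rule from it for the 24-week limit, so the citation alone cannot be shown to close the gap.

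The omission and the arithmetic stand. The consequence is weaker than it looks:

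- The CBR values in Section 15.2.2 are hoped-for observed rates, not decision limits, and the B2 target already lies inside its historical range. Two points in B1 is one patient of 50.
- How the historical studies dated stable disease is unknown here, so no reading can be shown to make the comparison fairer.
- Nothing in Section 15.5 ties CBR to PFS dating. Counting a patient whose week-24 scan shows progression as having reached 24 weeks of stable disease is strained.
- No passage supports a 7-day allowance. It would relax the stated limit and, as shown above, be more favourable than the strict count.

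**Conclusion.** No change to the plan is needed. Sections 15.2.2 and 15.5 leave a visit-window convention unwritten, and analysts can fill it sensibly when they program a descriptive table: count from Cycle 1 Day 1, use scans that show no progression, and state the convention with the result. The plan also provides for PFS to be listed for Phase IIa patients when appropriate, which would help a reader identify those near the limit.

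Under exponential progression and third scans spread over day 168 ± 7, the choice between the two plausible readings is worth about 5 points in B1 and 4 in B2. Both lie well inside interval widths of 19.8 and 27.0 points. Scan timing is not reported, so the real difference could be smaller; it is nil if every scan falls on day 168, and larger if most fall early. Cohort A is judged on objective response and is unaffected. Phase IIa enrollment is complete and development has been halted, so a rule added now would be late and would not improve the design.

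The 8-weekly scan line in the Synopsis is carried-over text that disagrees with Section 11.1.8 and Appendix 2. It is a clerical slip to reconcile at any next edit, with no effect on how CBR is defined.
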